Protocol: Informed consent will be obtained by the co-investigators using a written consent form approved by the Institutional Review Board. After informed consent is obtained, patients will receive: physical examination of both forearms; and a vascular Doppler to determine cephalic vein diameters of the nondominant arm. A 10 mL blood sample will be drawn at the next routine phlebotomy.

Patients will be asked to apply the Fist Assist[®] to the upper half of the non-dominant arm. Patients will be asked to use the device twice daily for two 2-hour periods, and report any complications or problems, using a log (see log attached at end of References). Patients will have follow up examinations with measurement of cephalic vein diameter at three months after enrollment.

Outcomes: The primary outcome will be the difference in vein diameter before and after Fist Assist[®] use. Secondary outcomes include: whether or not an AVF was created (versus a synthetic graft or use of a central venous catheter), whether the

resultant vascular access matured sufficiently to be used for HD, and the subsequent exposure of patients to central venous catheters during their first year of HD.

DURATION OF STUDY: All subjects will be enrolled and treated for three months. The duration of the study including data analysis and statistical analysis is expected to be 6-9 months.

| Table 1. Timeline for Study | | | |
|-----------------------------|----------|---------|--|
| Measurement | Baseline | Post-Rx | |
| H&P | Х | | |
| Clinical | Х | Х | |
| examinations | | | |
| Blood sample | Х | Х | |
| Doppler | Х | Х | |

DATA MANAGEMENT: Study data will be collected and managed using REDCap electronic data capture tools hosted at The University of Chicago.

STATISTICAL ANALYSES: The primary outcome of interest will be the difference in the diameter of the cephalic vein between baseline (Pre) and 3 months (Post) in patients treated with the Fist Assist[®] device. Based on prior work, mean vein diameters at baseline are anticipated to be approximately 1.8 mm with a standard deviation of 0.5 mm,⁴⁴ and we anticipate that the standard deviation of the change in diameter is likely to be approximately 0.75 mm.

Effect =[(DsPost)-(DsPre)]

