We would consider calculated effect sizes of 0.25-1.0 mm to be clinically meaningful changes that would increase the numbers of patients with vein diameters that meet commonly accepted thresholds for surgical suitability (normally 2.5-3.0 mm). Sample size calculations for a variety of effects are presented in table 1 (below), based on paired t-tests with alpha error of 0.05, standard deviation of the effect size of 0.75 mm, for power of 80% and 90%.

| Table 2 . Sample size required tocompare vein size before and aftertreatment | | | | |
|---|-------|-------|--|--|
| Effect size mm) | 80% | 90% | | |
| | power | power | | |
| 0.25 | 73 | 97 | | |
| 0.50 | 21 | 27 | | |
| 0.75 | 11 | 14 | | |
| 1.00 | 8 | 9 | | |
| 1.25 | 6 | 7 | | |
| 1.50 | 5 | 6 | | |

A secondary aim will be to compare the proportions of treated patients who achieve 3month vein diameters of 2.5 mm and 3.0 mm, to proportions achieved among controls. Given a normal distribution around a mean vein diameter of 1.8 mm with a standard deviation of 0.5 mm, the probability of an untreated wrist vein exceeding 2.5 mm (or 3.0 mm) would be 8.1% and 0.8%, respectively. Given that the standard deviation of the diameter of treated veins is at least 0.75, then the observed probabilities of a treated vein exceeding either 2.5 mm or 3.0 mm can be calculated, and is shown in the table below, any of which could be shown to be a significantly different proportion from the baseline state. The sample sizes required to demonstrate a difference in proportions were calculated using a McNemar test of paired proportions, with the very conservative assumption that 10% of veins that are adequate on preliminary measurement may fall below the cut-off value, due to variation in measurements.

| Table 3. Sample sizes required to demonstrated increased proportions of | | | | | | |
|---|---------|-----------------|-------|---------|-----------------|-------|
| surgically adequate veins | | | | | | |
| Effect | % veins | Required sample | | %veins | Required sample | |
| size | >2.5 mm | 80% | 90% | >3.0 mm | 80% | 90% |
| | | power | power | | power | power |
| 0.25 | 27.4 | 42 | 55 | 10.2 | 83 | 110 |
| 0.50 | 39.6 | 24 | 31 | 17.6 | 45 | 59 |
| 0.75 | 47.5 | 19 | 24 | 27.4 | 28 | 36 |
| 1.00 | 68.8 | 11 | 14 | 39.6 | 18 | 23 |
| 1.25 | 77.9 | 9 | 11 | 47.5 | 15 | 18 |
| 1.50 | 85.3 | 8 | 9 | 68.8 | 9 | 11 |

We intend to study 90 patients, and anticipate effects which should be more than adequate for these purposes.

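### Table 3 prints five percentages that its own normal model does not give, eight sample sizes inherit the error, and its 10% loss is not very conservative at the SD the table uses (minor; secondary aim, N=90 stands)

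*Combined protocol and SAP*

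**What the plan says.** The STATISTICAL ANALYSES section gives the planning values: "mean vein diameters at baseline are anticipated to be approximately 1.8 mm with a standard deviation of 0.5 mm", and "we anticipate that the standard deviation of the change in diameter is likely to be approximately 0.75 mm". It then states "We would consider calculated effect sizes of 0.25-1.0 mm to be clinically meaningful changes".

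For the secondary aim it takes a normal distribution, computes 8.1% and 0.8% of untreated wrist veins above 2.5 and 3.0 mm, and moves to treated veins: "Given that the standard deviation of the diameter of treated veins is at least 0.75, then the observed probabilities of a treated vein" exceeding each cut-off are set out in Table 3. Three of its rows read (effect; % above 2.5 mm, n at 80% and 90% power; % above 3.0 mm, n at 80% and 90% power):

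- "0.75 | 47.5 | 19 | 24 | 27.4 | 28 | 36"
- "1.00 | 68.8 | 11 | 14 | 39.6 | 18 | 23"
- "1.25 | 77.9 | 9 | 11 | 47.5 | 15 | 18"

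The sample sizes come from a McNemar test "with the very conservative assumption that 10% of veins that are adequate on preliminary measurement may fall below the cut-off value", which the plan attributes to measurement variation. After the table, the section concludes that 90 patients should be more than adequate.

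**The concern.** Two things in Table 3 do not fit the model stated above it.

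First, at an effect of 0.75 mm the assumed mean is 1.8 + 0.75 = 2.55 mm, already above the 2.5 mm cut-off. At 1.25 mm it is 3.05 mm, above 3.0 mm. A normal distribution must then put more than half the veins above the cut-off, yet both cells print 47.5%. If the percentages are wrong, so are the sample sizes computed from them.

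Second, the 10% loss is called very conservative, but the loss is not a free choice once the SDs before treatment, after treatment and of the change have been fixed.

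At stake is the arithmetic behind the statement that 90 patients suffice for the surgical-suitability aim.

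**Working it through.** **Inputs (all from STATISTICAL ANALYSES).** Baseline mean 1.8 mm, SD 0.5 mm; SD of change 0.75 mm; treated SD 0.75 mm (the stated minimum); effects 0.25 to 1.50 mm; 10% loss; power 80% and 90%. Alpha 0.05 is stated for Table 2. Taking it as two-sided for Table 3 is an assumption, supported by the reproduction in step 2.

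**1. Percentages.** P(above c) = 1 − Φ((c − 1.8 − effect)/0.75). The baseline figures reproduce: 1 − Φ(0.7/0.5) = 8.1% and 1 − Φ(1.2/0.5) = 0.8%.

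| Effect (mm) | >2.5 mm printed | >2.5 mm model | >3.0 mm printed | >3.0 mm model |
|---|---|---|---|---|
| 0.25 | 27.4 | 27.4 | 10.2 | 10.3 |
| 0.50 | 39.6 | 39.5 | 17.6 | 17.5 |
| 0.75 | **47.5** | 52.7 | 27.4 | 27.4 |
| 1.00 | **68.8** | 65.5 | 39.6 | 39.5 |
| 1.25 | **77.9** | 76.8 | **47.5** | 52.7 |
| 1.50 | 85.3 | 85.7 | **68.8** | 65.5 |

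Six cells agree to about 0.1 point, which shows that SD 0.75 was used. Five miss by 1.1 to 5.2 points, and 85.3 misses by 0.4. A larger SD does not help: 68.8 needs SD 0.30/0.490 = 0.61, 77.9 needs 0.55/0.769 = 0.72, and 47.5 has no solution.

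**2. Reproducing the printed n.** n = [1.96√pd + z√(pd − d²)]²/d², with p10 = 0.10 × p(pre), p01 = p(post) − p(pre) + p10, pd = p10 + p01, d = p01 − p10, and z = 0.842 or 1.282. The printed percentages return 23 of the 24 printed n after rounding up; the other is 18.04 against a printed 18. For example, at 0.75 mm and >2.5 mm with 47.5%: p10 = 0.0081, p01 = 0.4023, d = 0.3942, pd = 0.4104, giving 18.17, so 19 as printed.

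**3. Corrected n, same method and 10% loss.** In the same cell with 52.7%: p01 = 0.4539, d = 0.4458, pd = 0.4620, giving 15.65, so 16.

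| Cell | Printed 80%/90% | Computed | Corrected |
|---|---|---|---|
| 0.75 mm, >2.5 mm | 19/24 | 15.65/19.92 | 16/20 |
| 1.00 mm, >2.5 mm | 11/14 | 11.35/14.14 | 12/15 |
| 1.25 mm, >2.5 mm | 9/11 | 8.88/10.80 | 9/11 (unchanged) |
| 1.25 mm, >3.0 mm | 15/18 | 12.53/15.73 | 13/16 |
| 1.50 mm, >3.0 mm | 9/11 | 9.38/11.48 | 10/12 |

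Eight n change: four were too large and four too small. The rest stay within 1 of print; unrounded percentages move 110 to 109 and 59 to 60, which is rounding only.

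**4. Loss implied by the SDs.** From SD(change)² = SD(pre)² + SD(post)² − 2r·SD(pre)·SD(post), r = (0.25 + 0.5625 − 0.5625)/(2 × 0.5 × 0.75) = 1/3. Under bivariate normality, the loss P(post ≤ 2.5 | pre > 2.5), with SD of change held at 0.75, is:

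| Treated SD | r | 0.25 mm | 0.50 mm | 0.75 mm | 1.00 mm |
|---|---|---|---|---|---|
| 0.75 (Table 3) | 0.33 | 49% | 36% | 24% | 14% |
| 0.90 | 0.55 | 27% | 18% | 10% | 6% |
| 1.00 | 0.69 | 14% | 8% | 4% | 2% |

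**5. Power at N=90.** Power = Φ((d√90 − 1.96√pd)/√(pd − d²)). The weakest cell is 0.25 mm at 3.0 mm. As printed (10.2%, 10% loss): d = 0.0938, pd = 0.0954, so Φ(0.2845/0.2943) = Φ(0.967), about 83%. With the loss implied at treated SD 0.75 it is about 80%; at treated SD 0.90 and 1.0 it is about 95% and 98%. The next lowest cell is 98% with the 10% loss (0.50 mm at 3.0 mm) and 95% with the implied loss at SD 0.75 (0.25 mm at 2.5 mm).

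**The case against.** The percentage errors cannot be put down to PDF extraction. Two of the wrong values recur in both columns, and the printed n follow from them. The case on the other side concerns the loss rate and the weight of the point, and much of it stands.

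- **The treated SD is a lower bound.** The plan says at least 0.75, so the 49% to 14% is what the plan's SDs give at the edge that Table 3 uses. Step 4 shows the loss falling as that SD rises. This stands as a limit on the claim. It does not rescue the label: the table's percentages are computed at 0.75, and a larger SD would change all of them.
- **The 3.0 mm losses.** The same calculation gives 65%, 51%, 37% and 25% at 3.0 mm, and a reader might infer that the plan implies losses of up to 65%. The documents do not support that. The exclusion criteria under SUBJECTS remove patients with a superficial vein above 3.0 mm in the lower arm, so this loss has almost no eligible denominator. At 2.5 mm the restriction matters little: limiting baseline to 2.5–3.0 mm gives 51%, 37%, 25% and 15%.
- **Measurement variation.** The plan offers the 10% as an allowance for measurement variation only. That explains where it comes from, but a McNemar calculation needs the total loss, whatever its cause.
- **Large effects.** Above 1.00 mm the implied loss at 2.5 mm is below 10% (7.8% and 3.8%). That lies outside the range the plan calls clinically meaningful.
- **Materiality.** No n moves by more than 4, the aim is secondary, and Table 3 already prints 110 for 90% power in the weakest cell. This stands, and it makes the point minor.

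**Conclusion.** Table 3 is wrong as written, with minor consequences. The finding on the five percentages and eight sample sizes is firm: it needs only the plan's own normal model at SD 0.75 and the McNemar method that reproduces its printed n. The impossibility of 47.5% holds at any SD.

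The finding on the loss is conditional. At the treated SD used in Table 3, with the stated baseline and change SDs and bivariate normality, 10% is below the implied loss at 2.5 mm throughout 0.25–1.00 mm, so the description as very conservative is not justified. It does not follow that 10% is too low at every treated SD the plan allows.

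A reader might also infer that 90 patients are too few. The documents do not support that: power is about 95% or more in every cell but one, and in that one it is about 80% to 83% at treated SD 0.75 and higher if that SD is larger. Nor is the primary paired comparison touched, since Table 2 uses neither these percentages nor the loss rate.

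**What to change.** 1. In Table 3, change 47.5 to 52.7 and 68.8 to 65.5 (both columns), 77.9 to 76.8, and 85.3 to 85.7 (no effect on n).
2. Replace the eight n with the corrected values in step 3 of the working.
3. Delete the description of the 10% loss as very conservative. Keep 10% as a plain assumption, and add a short sensitivity range at 2.5 mm over effects of 0.25 to 1.00 mm: 49% to 14% at treated SD 0.75, 27% to 6% at 0.90, and 14% to 2% at 1.0. A second full set of sample sizes is not needed.
4. Qualify the closing sentence, for example: *For a 0.25 mm effect at the 3.0 mm cut-off, 90 patients give about 83% power with a 10% loss (about 80% with the loss implied at a treated SD of 0.75, higher if that SD is larger), fewer than the 110 shown for 90% power; every other cell of Table 3 has about 95% power or more.*

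The cost is recalculation and a few lines of text. The design, N=90 and Table 2 do not change.

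### The secondary aim compares vein-size proportions with undefined controls, while Table 3 sizes a before/after test, so 90 patients is not shown to be adequate for the stated comparison

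*Combined protocol and SAP*

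**What the plan says.** The secondary aim in STATISTICAL ANALYSES compares treated patients' three-month "diameters of 2.5 mm and 3.0 mm, to proportions achieved among controls". The proportions that follow are described differently, as "any of which could be shown to be a significantly different proportion from the baseline state", and Table 3's sample sizes were "calculated using a McNemar test of paired proportions". They allow for 10% of initially adequate veins dropping below the cut-off.

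Two spreads are used. Untreated veins are "Given a normal distribution around a mean vein diameter of 1.8 mm with a standard deviation of 0.5 mm". For treated veins the text reads "Given that the standard deviation of the diameter of treated veins is at least 0.75". The same section says of the paired change that "the standard deviation of the change in diameter is likely to be approximately 0.75 mm". Table 3's smallest-effect row is "0.25 | 27.4 | 42 | 55 | 10.2 | 83 | 110": percentage above 2.5 mm, N for 80% and 90% power, then the same three figures for 3.0 mm. The sizing conclusion is "We intend to study 90 patients, and anticipate effects which should be more than adequate for these purposes".

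Elsewhere, SUBJECTS (Inclusion criteria) assigns patients to the device. METHODOLOGY (Intervention) mentions a randomization code but gives the device to every subject. METHODOLOGY (Doppler) has both arms scanned at baseline and at the end of therapy, whereas METHODOLOGY (Protocol) has the post-consent scan on the non-dominant arm only. The secondary outcomes listed under Outcomes do not include this comparison.

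**The concern.** The comparison named is not the comparison sized. Controls could mean a parallel group, the untreated arm or the baseline scan. Each needs a different analysis and has different power, and the plan does not choose. An analyst could settle the question after seeing the data.

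The two SDs add a second problem. A wider distribution puts more veins above a high cut-off even if the average vein has not changed. Part of the rise that Table 3 is built to detect is therefore assumed spread rather than average dilation. A before/after test cannot tell whether extra spread comes from measurement variation (which the plan itself mentions), the passage of time or a varied response to the device. A significant secondary result could be read as showing that the device makes veins surgically usable when the design cannot support that.

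**Working it through.** **1. Reproduce Table 3, 0.25 mm row.** The proportion above cut-off c is 1 − Φ((c − mean)/SD).
- Untreated, mean 1.8, SD 0.5: z = 1.4 gives 8.08%; z = 2.4 gives 0.82%.
- Treated, mean 2.05, SD 0.75: z = 0.60 gives 27.43%; z = 1.267 gives 10.26%.

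The McNemar normal formula is n = [1.96√s + z_β√(s − d²)]²/d². Here p10 = 0.1 × baseline proportion, d = treated − baseline proportion, p01 = d + p10 and s = p01 + p10. Alpha is 0.05; the plan does not state sidedness, but two-sided reproduces the table.
- 2.5 mm: p10 = 0.0081, p01 = 0.2011. n = 41.6 and 54.7, so 42 and 55, as printed.
- 3.0 mm: p10 = 0.0008, p01 = 0.0948. n = 82.5 and 109.5, so 83 and 110, as printed.

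**2. Compare 90 with the plan's own entries.** The largest 80% entries are 73 (Table 2) and 83 (Table 3); 90 exceeds both. The 90% entries at 0.25 mm include 97 (Table 2) and 110 (Table 3, 3.0 mm); 90 is below both. For the primary paired t-test, noncentrality is (0.25/0.75)√90 = 3.16 and power is 87.9%.

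**3. Change the SD only (mean 1.8, SD 0.75).** z = 0.933 gives 17.53%; z = 1.6 gives 5.48%. The rises are 9.46 and 4.66 points.

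**4. Share of the 0.25 mm row due to spread.** The total rises are 19.35 and 9.44 points.
- SD change first: 9.46/19.35 = 49%; 4.66/9.44 = 49%.
- Mean shift first (mean 2.05, SD 0.5: 18.41% and 2.87%): 9.02/19.35 = 47%; 7.39/9.44 = 78%.

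Above 2.5 mm the share falls to 30% or 16% at 0.50 mm, depending on order. With the mean shift first it is slightly negative at 0.75 mm (−3%) and 1.00 mm (−12%).

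**5. Before/after test at N = 90 with no mean dilation (exact McNemar).**
- With the plan's 10% rule: 75% (2.5 mm) and 24% (3.0 mm).
- With the pre/post correlation implied by SDs 0.5 and 0.75 and SD of change 0.75, (0.25 + 0.5625 − 0.5625)/(2 × 0.5 × 0.75) = 1/3: 45% and 23%.

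The normal approximation gives 78% and 52%, or 53% and 44%. It is unreliable at 3.0 mm, where only about 4 to 5 discordant pairs are expected. The exact two-sided test needs at least 6, since 2 × 0.5⁵ = 0.0625 and 2 × 0.5⁶ = 0.031.

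**6. Power against an untreated arm at 3 months.** N = 90, means 1.8 and 2.05, bivariate normal, McNemar normal approximation. The between-arm correlation of 0 to 0.8 and the untreated three-month SD are assumptions; the plan gives neither.

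| SD untreated / treated | Above 2.5 mm | Above 3.0 mm |
|---|---|---|
| 0.75 / 0.75 | 35–63% | 22–36% |
| 0.5 / 0.5 | 53–77% | 17–22% |
| 0.5 / 0.75 | 92–99% | 78–84% |

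The overall ranges are 35–99% and 17–84%. Exact McNemar on the same inputs lowers the bottom ends to about 28% and about 2%. The latter reflects roughly 90 × (0.0082 × 0.9713 + 0.0287 × 0.9918) = 3.3 expected discordant pairs at zero correlation.

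**7. If a parallel group was meant.** Assume 1:1 allocation (45 per group) and Table 3's own percentages. Power at 0.25 mm is then 67% (2.5 mm) and 50% (3.0 mm).

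**The case against.** For the before/after test that Table 3 sizes, 90 is adequate at 80% power on the plan's inputs. At 0.25 mm, power is 99% (2.5 mm) and 83% (3.0 mm) with the 10% rule, or 95% and 80% with correlation 1/3. This stands. A reader might infer that 90 is too few for that test; the documents do not support that.

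A reader might also treat the 0.75 mm as a mistaken reuse of the SD of the change. The figures do not establish that. If the change were independent of baseline, the post-treatment SD would be √(0.25 + 0.5625) = 0.90, so at least 0.75 is compatible with the plan's other input. Varied response to the device is also a legitimate source of spread. It is tempting to hold SD 0.5 at both visits, which gives 86 instead of 42 and about 411 instead of 83 for 80% power. With an SD of change of 0.75, that requires a pre/post correlation of (0.25 + 0.25 − 0.5625)/0.5 = −0.125. Those sizes discard a stated input and do not correct Table 3.

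The rates in step 5 should not be read as ordinary false-positive rates: under those inputs the proportions really do rise. What is in doubt is the cause.

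Finally, replacing controls with baseline would make the text consistent, and the lack of a concurrent comparator limits the primary outcome too. Both are true. But that wording alone would leave a before/after result open to being read as a device effect, although METHODOLOGY (Doppler) already collects a concurrent comparator.

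**Conclusion.** The point holds as a problem of comparator and attribution, not of sample size arithmetic in the 0.25 mm row, which reproduces exactly. The stated comparison has no defined control and is not the one sized. The claim that 90 is more than adequate is unsupported for it, and it overstates the tests that are sized, given the plan's own 97 and 110.

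In the 0.25 mm row, assumed spread supplies 47–49% of the rise above 2.5 mm and 49–78% above 3.0 mm, depending on the order of attribution. A reader might carry the figure of about half over to the whole table; above 2.5 mm it shrinks quickly at larger effects. Whether 90 suffices against an untreated arm at 0.25 mm turns on an SD and a correlation that the plan does not give.

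The calculations assume normal diameters, 90 patients with usable scans, equal untreated means in the two arms for step 6, and no truncation from the 1.0–3.0 mm entry screen. Table 3 ignores that screen too, and it matters most for the 3.0 mm figures. The primary outcome's sizing is not affected.

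**What to change.** 1. Reconcile SUBJECTS, METHODOLOGY and STATISTICAL ANALYSES on whether controls exist and which arms are scanned at baseline. If a separate control group is intended, define it and state the power of a two-group test at the planned size.
2. If the trial is single-arm, name a comparator that it measures. Suggested text: *The proportions of treated arms above 2.5 mm and above 3.0 mm at 3 months will be compared with the same patient's untreated arm at 3 months (McNemar test). Baseline proportions will be shown for both arms. Pre/post changes in proportions are descriptive and will not be taken as evidence of a device effect.* Add this comparison to the secondary outcomes under Outcomes.
3. Replace the sizing sentence with: *90 scanned patients give 88% power for a mean change of 0.25 mm (SD of change 0.75 mm). Power for the between-arm proportions at 0.25 mm depends on the assumed untreated 3-month SD and between-arm correlation.* Give the range from step 6 (35–99% above 2.5 mm, 17–84% above 3.0 mm, correlation 0 to 0.8), and say whether the test is exact or approximate.

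Cost: no extra patients. No extra scans are needed if the Doppler paragraph governs; if the Protocol paragraph governs, the dominant arm must also be scanned at baseline. The stated power for the secondary aim becomes less favourable. The two arms may differ before treatment, which is why both baselines must be shown.
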